#### 1.3 Study Objectives

#### Primary Objective

• To assess efficacy of assay-guided treatment (AGT) versus treatment-as-usual (TAU) in Major Depressive Disorder, as measured by change in Hamilton Depression Rating Scale (SIGH-D-17) at 8 weeks.

#### Secondary Objectives

- To assess efficacy of assay-guided treatment (AGT) versus treatment-as-usual (TAU) in Major Depressive Disorder, as measured by change in Quick Inventory of Depressive Symptoms (QIDS-SR16) at 8 weeks.
- To assess the percentage of responders at Week 8, based on SIGH-D-17, QIDS-SR16, and Clinical Global Impression–Improvement (CGI-I), respectively. Treatment response will be defined in 3 different ways:
  - Blinded Rater Assessment: ≥ 50% reduction from baseline of SIGH-D-17 score ;
  - Subject-Rated Assessment: ≥ 50% reduction from baseline of QIDS-SR16;
  - Unblinded Clinician Assessment: ≤ 3 score on the CGI-I;
- To assess the percentage of remitters at Week 8, based on the SIGH-D-17 and QIDS-SR16, respectively. Remission is defined for the SIGH-D-17 and the QIDS-SR16:
  - Blinded Rater Assessment: ≤ 7 score on the SIGH-D-17;
  - Subject-Rated Assessment: ≤ 5 score on the QIDS-SR16
- To assess the impact of the Genecept Assay ™ on adverse events, based on Frequency, Intensity and Burden of Side Effects Rating (FIBSER) and Patient-Related Inventory of Side Effects (PRISE), frequency and severity of adverse events and Columbia-Suicide Severity Rating Scale (C-SSRS) outcomes.
- After completion of the main MDD study, to conduct the Exploratory Elderly MDD Study, to preliminarily assess the efficacy and safety of AGT vs TAU in the elderly, age  $\geq$  65. This study will provide additional data on this important, Medicare-eligible population, which is sparsely represented in the Main Study (< 8% of subjects). As specified in Protocol Amendment 2, after the Main Study enrollment finishes, approximately 70 subjects, age  $\geq$  65, will be randomized to the this add-on study. Except for change in age of inclusion, all study procedures will be identical to the Main Study. Primary efficacy will be measured by change in Hamilton Depression Rating Scale (SIGH-D-17) at 8 weeks.

#### 1.4 Randomization

Approximately 300 for the main study, plus an additional 70 subjects age  $\geq$  65 for the Exploratory Elderly MDD Study, will be randomized in a 1:1 ratio to receive Assay-Guided Treatment (AGT) or Treatment as Usual (TAU). Randomization will be stratified by site, using a variable block size randomization to minimize bias. Randomization will be completed via IWRS during the Baseline visit, after Screening and Baseline inclusion/exclusion criteria have been satisfied.

## 2 STATISTICAL AND ANALYTICAL PROCEDURES

**Note:** Unless stated otherwise, this section applies to both the Main Study and the Exploratory Elderly MDD Study. Procedures, in general, may be adjusted in the Exploratory Elderly MDD Study to reflect sparse sample sizes, eg, substitution of a short listing in place of a full table.

Summarizations will be provided in tables and figures. Safety and efficacy variables will be summarized by visit using descriptive statistics. For continuous variables, this will include the number of non-missing values, mean, standard deviation (SD) or standard error of the mean, median, minimum, and maximum. Categorical variables will be summarized using counts and percentages.

Unless otherwise stated, the significance level for statistical tests will be two-sided, alpha=0.05, with no adjustment for multiple comparisons

Pooled Investigative Sites: For all statistical analyses, sites with few subjects (< 7 subjects) will be pooled into a single larger site. "Investigative site" in all statistical analyses will refer to "sites" as pooled.

SIGH-D-17 interviews will be reviewed by central expert monitors, and site SIGH-D-17 scores may be revised based on the central monitor evaluation. All SIGH-D-17 changes due to central review will be described by listings. SIGH-D-17 statistical analyses, summaries, and listings will otherwise rely solely on the revised SIGH-D-17 scores. Note, SIGH-D-17 inclusion criteria are based on the original site rater screening and baseline SIGH-D-17, irrespective of any later revision after central review.

**Note:** No central rater evaluation will be done for the Exploratory Elderly MDD Study, as the sites enrolling subjects will continue from the Main Study and already have trained, experienced site raters.

Data will be reported and analyzed using SAS software, version 9.3, except as noted otherwise.

#### 2.1 Efficacy Analysis Estimands

This trial is a comparison of outcomes between two treatment strategies, evaluated at 8 weeks. For practical interpretation, this implies the statistical analyses should estimate and test the difference in Week 8 outcomes for all subjects, irrespective of attrition or compliance. [This may also be described as following the Intent to Treat (ITT) principle, but there is confusion about the use of this term when there is missing data, and ITT terminology will not be used further here.]. Specifying the "estimands") (what is being estimated), aligned with the study purpose, is the basis for the formal statistical methods which follow.

### Primary Efficacy: AGT vs TAU

• -Difference at Week 8 in SIGH-D-17 mean change from baseline, for all randomized subjects.

### Secondary Efficacy: AGT vs TAU

- Difference at Week 8 in QIDS-SR16 mean change from baseline, for all randomized subjects.
- Difference in % treatment responders at Week 8, for all randomized subjects. Treatment response will be defined in 3 different ways:

 $\geq$  50% reduction of SIGH-D-17 from baseline for blinded rater assessment

≥ 50% reduction of QIDS-SR16 from baseline for subject-rated assessment

Score of  $\leq$  3 on the CGI-I from baseline for the unblinded clinician assessment

• Difference in % treatment remitters at Week 8, for all randomized subjects. Remission is defined for the SIGH-D-17 and the QIDS-SR16:

Score of  $\leq$  7 on the SIGH-D-17 from baseline for blinded rater assessment

Score of  $\leq$  5 on the QIDS-SR16 from baseline for subject-rated assessment.

### Other Efficacy

- Difference at Week 8 in mean % improvement from baseline in SIGH-D-17 scores, for all randomized subjects.
- Difference at Week 8 in mean % improvement from baseline in QIDS-SR16 scores, for all randomized subjects.
- Difference at Week 8 in CGI-I % scores, for all randomized subjects.
- Difference at Week 8 in CGI-S Change from baseline scores, for all randomized subjects.

### 2.2 Safety Endpoints

- Treatment Emergent Adverse Events (TEAEs)
- Frequency and severity of medication-induced side effects based on collection of FIBSER, PRISE and Adverse Events
- Columbia-Suicide Severity Rating Scale (C-SSRS) Change from baseline.

## 2.3 Other Endpoints

- Clinical Decision Survey Findings
- Pre-Result: Clinician intended treatment prior to receiving assay results
- Post-Result (AGT only): Clinician rating of confidence in making treatment decisions, treatment plan and gene results which influenced treatment plan after results were received.

# **3 STATISTICAL METHODS**

**Note:** Unless stated otherwise, this section applies to both the Main Study and the Exploratory Elderly MDD Study. In general, in the Exploratory Elderly MDD Study analyses may be adjusted to reflect sparse sample sizes, e.g., substitution of a short listing in place of a full table.

The efficacy analyses for the Exploratory Elderly MDD Study are specified at the end of the Efficacy *Analyses, Section 3.4*.

## 3.1 Subject Disposition

The number of subjects will be summarized by treatment group and study center for the three analysis datasets. Randomized subjects excluded from the SAF and FAS populations will be listed. The number and percentage of subjects per treatment group who prematurely discontinued treatment will be presented by visit and overall, by treatment group, for SAF population. The number and percentage of subjects per treatment group who prematurely discontinued from the study will be presented by visit and overall, for the SAF and FAS populations. A CONSORT style (Ref) flow chart will describe premature study discontinuation for the FAS population. The coded Reason for Premature Discontinuation will be summarized (number and percentage) by treatment group for the FAS Population. The verbatim Reason for Discontinuation and Additional Information text entries

will be listed. The coded Reason for Discontinuation and verbatim Reason for Discontinuation and Additional Information may be used in sensitivity analyses for the primary efficacy analysis.

#### 3.2 Demographic and Pretreatment Characteristics

Demographics (age, race, sex, weight, height, and BMI), disease severity [including SIGH-D-17 at screening and baseline; QIDS-SR16 and CGI-S at baseline], number of failed, adequate treatment regimens in the current MDD episode (1 vs > 1), previous depression treatment/history, and other screening/baseline visit assessments will be summarized by visit (Screening, Baseline) and treatment group using descriptive statistics. The number of failed, adequate treatments will be considered to be > 1 if two or more standard MDD medications (FDA approved for MDD or approved by the sponsor as commonly used for MDD) are entered in the eCRF as "ATRQ Failed Medications," with daily dose greater than or equal to the minimum MDD dose, and given for at least 6 weeks.

#### 3.3 Depression Treatment and Concomitant Medications

#### **Depression Drug Treatment**

On-study depression drugs (taken between Day 0 and Week 8 visit) will be summarized by the number and proportion of subjects in each treatment group receiving each medication within each drug class, for the Safety Population. Treatment Exposure (days) to on-study depression drugs (days) from Day 0 to Week 8 will be summarized for the Safety Population by treatment group and drug class. Descriptive statistics (n, mean, standard deviation, minimum, median, and maximum) will be presented.

#### **Concomitant Medications**

CNS drugs (taken between Day 0 and Week 8 visit) will be summarized by the number and proportion of subjects in each treatment group receiving each medication within each drug class, for the Safety Population. Multiple medication use by a subject will be counted only once.

All other concomitant medications use (medication taken between Day 0 and Week 8 visit) will be listed. Additional summarizations may be done to help interpret study findings.

#### 3.4 Efficacy Analyses

**Note**: The Efficacy Analyses for the Exploratory Elderly MDD Study will be given at the end of this section. Generally, the statistical methods for the Exploratory Elderly MDD Study will follow the outline of the Main Study, but will be primarily descriptive, and statistical analyses will be simpler, as necessitated by the smaller sample size.

#### Primary Endpoint Analyses

A Mixed Model Repeated Measures (MMRM) analysis will test whether AGT shows greater improvement in SIGH-D-17 at Week 8 than TAU. Formally, the analysis tests for a difference in mean change from baseline to Week 8 between the treatment groups, in the FAS population. Compared to analyzing All Randomized subjects, this excludes subjects who don't return after the Baseline Visit, which is generally acceptable, if this excluded group is small. In the MMRM model, the dependent variable is the change in SIGH-D-17 from baseline at each of the scheduled visits Week 2, Week 4, Week 6 and Week 8. The model will include the fixed effect continuous factor baseline SIGH-D-17, and fixed effect categorical factors investigative site, treatment group (AGT and TAU; 2 levels), visit (Weeks 2, 4, 6 and 8; 4 levels), and treatment x visit interaction. The interaction term will remain in the model regardless of statistical significance. An unstructured covariance pattern will be used to estimate the variance-covariance matrix of the within-subject repeated measures (i.e., model within-subject errors). The variance-covariance matrix will be estimated across both treatment arms. The fixed effects will be estimated by the method of restricted maximum likelihood estimation using the Newton-Raphson algorithm, based on all available data. The denominator degrees of freedom and adjustment of standard errors will use the Kenward-Roger method.

Assignment of SIGH-D-17 assessments to Visit for primary MMRM analysis:

Day 7-20 SIGH-D-17 => Week 2 Visit Day 21-34 SIGH-D-17 => Week 4 Visit Day 35-48 SIGH-D-17 => Week 6 Visit Day 49-70 SIGH-D-17 => Week 8 Visit

If the final SIGH-D-17 assessment is on Day 1-6, this SIGH-D-17 value will be assigned to the Week 2 Visit. If multiple SIGH-D-17 assessments fall within a Visit assignment range, the assessment closest in time to the nominal visit day will be retained. For example, the in range assessment taken closest to Day 14 for Week 2 Visit, will be retained.

AGT and TAU mean change in SIGH-D-17 at Week 8 will be estimated and tested utilizing the least squares (LS) means from the treatment x visit interaction in the MMRM model. The primary analysis will test the difference (contrast) between the Week 8 LS means, at two-sided significance 0.05. The test p-value and the 95% CI for the difference in Week 8 means will be presented. Comparisons between the AGT and TAU means at Week 2, Week 4 and Week 6 will also be generated. Diagnostics for outliers, non-normality and other model assumptions will be run. Findings will be followed up with sensitivity analyses, as appropriate.

To allow comparison with previous SIGH-D-17 studies, two supportive analyses of the primary endpoint will be produced. Each will be an Analysis of Covariance (ANCOVA):

1) Last Observation Carried Forward (LOCF) analysis, and

2) Observed Cases (OC) analysis.

Each ANCOVA will include baseline SIGH-D-17, Investigative Site and Treatment Group as the independent variables in the model. The dependent variable for the LOCF analysis will be last available SIGH-D-17 change from baseline. The dependent variable for the OC analysis will be the Week 8 SIGH-D-17 score, with no imputation of missing Week 8 scores.

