Sample Size	Approximately 300 subjects will be randomized according to a 1:1 ratio to AGT or TAU.
	As specified in Protocol Amendment 2, after Main Study enrollment completes, an additional 70 subjects, age \geq 65, will be randomized according to a 1:1 ratio, to the Exploratory Elderly MDD Study. The Exploratory Elderly MDD Study will be analyzed as a separate study.
Study Sites	Multi-center, with approximately 25 sites in the US.
Location	The Exploratory Elderly MDD Study will include approximately 12 US sites.
Key Subject Eligibility Criteria	 Inclusion: Main Study: Age 18-75 years Exploratory Elderly MDD Study: Age ≥ 65 years Primary diagnosis of Major Depressive Disorder (without psychosis) based on DSM-5 criteria and MINI 7.0 SIGH-D-17 score ≥18 (i.e., moderate depression), at Screening and Baseline Failure of at least 1 prior adequate trial of a standard antidepressant for the current major depressive episode (using ATRQ criteria – i.e., 6 weeks at adequate dose) due to inefficacy, side effects, or intolerability
	 Severe personality traits (based on DSM-5 criteria) that in the opinion of the investigator may interfere with the participation in the study or the evaluation of efficacy and safety and all diagnosed Personality Disorders Current DSM-5 diagnosis of Neurocognitive Disorders, Schizophrenia Spectrum (lifetime diagnosis) and other Psychotic Disorders, Bipolar and related disorders (lifetime diagnosis), Trauma and Stress related Disorders, Obsessive Compulsive Disorder and Related Disorders. Other DSM-5 disorders that in the opinion of the investigator may interfere with the participation in the study or the evaluation of efficacy and safety. DSM-5 diagnosis of Substance Related and Addictive Disorders diagnosed in the last 12 months (other than tobacco and caffeine)

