Main Study: The sample (n=300) size is based on previous study findings comparing SIGH-D-17 improvement in MDD patients whose physician's treatment decision were informed (AGT) or not (TAU) by the results of a targeted suite of genetic assays.

The sample size calculation assumed a difference in SIGH-D-17 mean improvement scores = 3.1, the within-subject standard deviation (SD) = 7.2, a dropout rate at Week 8 of 23%, a two-sided 0.05 t-test of treatment means, and 90% power. These assumptions result in a sample size of 150 randomized patients in each treatment group (300 total).

Various alternate scenarios are presented in the Section 9 (Statistical Procedures). All calculations were made with Stata version 13 software. Note that all calculations should be somewhat conservative, since the actual primary analysis will be a MMRM analysis.

Add-on Exploratory Elderly MDD Study: Sample size (n=70) was not formally calculated for this exploratory study.

SCHEDULE OF VISITS AND PROCEDURES

Study Period	Screening	Day 0 / Baseline	Week 2	Week 4	Week 6	Week 8
Visit Windows	-7 days ^a	0 days	+/- 3	+/- 3	+/- 3	-5/+7
			days	days	days	days
Informed Consent	•					
Demographics	•					
Inclusion/Exclusion Criteria	•					
(MINI, ATRQ)						
Columbia Suicide Severity Rating	•	•	•	•	•	•
Scale (C-SSRS)						
Medical/Psychiatric History	•					
Urine Drug Screen Evaluation	•					
Concomitant Medications / MDD Treatment Medications	•	•	•	•	•	•
Adverse Events	•	•	•	•	•	•
Structured Interview Guide for the Hamilton Depression Rating Scale – 17 Item Version (SIGH-D-17) ^b	•	•	•	•	•	•
Quick Inventory of Depression		•	•	•	•	•
Symptoms (QIDS-SR16)						
Clinical Global Impression - Severity		•	•	•	•	•
(CGI-S) Clinical Global Impression - Improvement (CGI-I)			•	•	•	•
Frequency, Intensity, and Burden of Side Effects Rating (FIBSER)		•	•	•	•	•
Patient Rated Inventory of Side Effects (PRISE)		•	•	•	•	•
DNA Sample Collection ^c	•					
Randomization ^e		•				
Clinical Decision Survey Pre-Result ^{d,f}		•				
Genecept Assay TM Results Retrieval ^{d,f} / Results Review ^{f,g}		•				
Initiation or Adjustment of MDD Treatment ^f		•				
Clinical Decision Survey Post-Result ^{d,f}		•				
Disclosure of Treatment Group ^{c,f} a may be extended by up to 5 days		_	_			•

^a may be extended by up to 5 days

^b blinded rater

^c after all visit procedures have been completed

^d via Investigator Portal

^e after eligibility has been confirmed by SIGH-D-17 and C-SSRS

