1.1 Treatment of MDD

The importance of full symptomatic remission as a treatment goal in MDD is well established²⁶. As previously stated, about two-thirds of individuals with MDD fail to remit with an initial antidepressant trial of adequate dose and duration, and roughly half the latter group will not achieve remission despite as many as 3 more pharmacotherapeutic interventions^{7,27,28}. The probability of remission, in fact, declines sharply after each failed treatment trial: Remission rates in the STAR*D trial were 36.8%, 30.6%, 13.7%, and 13.0% for each successive treatment, and individuals with 2 or more failed trials were significantly more likely to experience early recurrence, even if they had improved on treatment²⁹.

MDD is the most frequent factor in years lived with disability in developed countries³⁰, and Treatment Resistant Depression (TRD) accounts for much of this disability^{6,31}. Among outpatients, the annual cost of care for TRD is \$10,241, versus \$6,512 for outpatients without TRD; these costs become higher when greater rates of hospitalization in TRD patients are factored in⁶. The cost to society in terms of lost productivity is likely to be even greater.

TRD, as mentioned earlier, is usually defined as treatment failure of two or more antidepressant trials of adequate dose and adequate duration^{32,33}. As suggested by the STAR*D outcomes cited above, treatment resistance in MDD patients is common and problematic.

The potential benefits of personalized pharmacotherapy for patients with MDD are well recognized in psychiatry. Given the proliferation of treatment options for MDD, patients can spend months or years in and out of various treatment regimens before receiving optimally effective pharmacotherapy. If pharmacogenetic profiles of MDD patients can be defined early in the course of their illness, these patients can receive more targeted interventions to improve likelihood of remission.

1.2 **Pharmacogenetic Testing**

Pharmacogenetic testing offers the promise of targeting patients more quickly to personalized treatments that are more likely to improve symptomatology and less likely to cause adverse effects. Genomind, Inc. provides a test for genotyping of gene variants (Genecept Assay TM) that are relevant to psychotropic drug response. For example, the short allele of the serotonin transporter gene (*SLC6A4*) is associated with antidepressant efficacy and side effects ¹⁶. This allele is addressed in the Genecept test.

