5 SUBJECT ENROLLMENT

Investigative sites will recruit the subjects. If a patient agrees to meet with the research team, the study team will speak with the patient and start the informed consent process.

The informed consent process begins with an assessment of the patient's ability to give informed consent. Clinician investigators will use their clinical judgment to make this determination. Family members or caregivers should be encouraged to be involved in the consent process and/or follow-up visits as appropriate. All aspects of the study, including genetic testing, medications, risks and benefits, will be explained to the patient in detail. Patients will have the study thoroughly explained and any questions will be answered. Only when patients are fully informed about the study, will they be asked to sign the informed consent document. Documentation about the subject's capacity to consent for the study and detailed notes about the consenting process will be placed into the subject's research chart.

At the Screening visit, site staff will log on to IWRS to register the subject and obtain a unique subject number that will serve as the subject's identification number on all study documents and case report forms.

After written informed consent and registration in IWRS, subjects will undergo screening procedures to determine eligibility for the study.

Eligible subjects will be randomized in a 1:1 ratio to receive Assay-Guided Treatment (AGT) or Treatment as Usual (TAU). Randomization will be stratified by site, using a variable block size randomization to minimize bias. Randomization will be completed via IWRS during the Baseline visit, after Screening and Baseline inclusion/exclusion criteria have been satisfied, including the SIGH-D-17 and C-SSRS Baseline assessments.

Each subject randomized will continue using the unique study identification number received at Screening which will be used on all study documentation and case report forms. The Genecept Assay TM results for subjects randomized to the AGT arm will be available via a secure portal to the treating investigator and will be provided upon completion of successful randomization in the IWRS system. Genecept Assay TM results will be made available to the treating investigator for every subject upon completion of the Week 8 visit.

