9.4 Efficacy Analyses

9.4.1 Primary Endpoint Analyses

A Mixed Model Repeated Measures (MMRM) analysis will test whether AGT shows greater improvement in SIGH-D-17 at Week 8 than TAU. Formally, the analysis tests for a difference in mean change from baseline to Week 8 between the treatment groups, in the FAS population. Compared to analyzing All Randomized subjects, this excludes subjects who don't return after the Baseline Visit, which is generally acceptable if this excluded group is small.

In the MMRM model, the dependent variable is the change in SIGH-D-17 from baseline at each of the scheduled visits Week 2, Week 4, Week 6 and Week 8. The model will include the fixed effect continuous factor baseline SIGH-D-17, and fixed effect categorical factors (pooled) investigative site, treatment group (AGT and TAU; 2 levels), visit (Weeks 2, 4, 6 and 8; 4 levels), and treatment x visit interaction. The interaction term will remain in the model regardless of statistical significance. An unstructured covariance pattern will be used to estimate the variance-covariance matrix of the within-subject repeated measures (i.e., model within-subject errors). The variance-covariance matrix will be estimated across both treatment arms. The fixed effects will be estimated by the method of restricted maximum likelihood estimation using the Newton-Raphson algorithm, based on all available data. The denominator degrees of freedom and adjustment of standard errors will use the Kenward-Roger method.

AGT and TAU mean change in SIGH-D-17 at Week 8 will be estimated and tested utilizing the least squares (LS) means from the treatment x visit interaction in the MMRM model. The primary analysis

will test the difference (contrast) between the Week 8 LS means, at two-sided significance 0.05. The test p-value and the 95% CI for the difference in Week 8 means will be presented. Comparisons between the AGT and TAU means at Week 2, Week 4 and Week 6 will also be generated. Diagnostics for outliers, non-normality and other model assumptions will be run. Significant findings will be followed up with appropriate sensitivity analyses.

To allow comparison with previous SIGH-D-17 studies, two supportive analyses of the primary endpoint will be produced. Each will be an Analysis of Covariance (ANCOVA):

- 1) Last Observation Carried Forward (LOCF) analysis, and
- 2) Observed Cases (OC) analysis.

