The three studies are consistent with one another. The small pilot studies show evidence of efficacy, but are too small for reliable inference. Study 1 greatest observed efficacy (Cohen's d =0.58). The second pilot study (Study 3), is more rigorous, adding randomization and rater/subject blinding, with extrapolated Cohen's d = 0.47, not statistically significant.

The largest study (Study 2) shows a somewhat lower Cohen's d (0.43), a more reliable result due to the much larger sample size and the added sensitivity analyses to assess robustness. Accepting that there remains potential bias due to the non-randomized, open design, this study result was used as the best available basis for sample size calculation.

The sample size is calculated for the two-sided alpha=0.05, 90% power test of two independent means of improvement in SIGH-D-17. In this case the sample size depends only on the postulated Cohen's d, and the % dropouts. Note this should be a conservative estimation of sample size, as the actual analysis will use a more efficient MMRM method. However, this conservatism is balanced by the potential underestimation of needed sample size due to design bias in the reference study.

Using the Trial 2 observed difference in SIGH-D-17 improvement and variability, with resulting Cohen's d=0.43, the resulting sample size is 115 per group, with no dropouts. If we assume the dropout rate somewhat less than the reference (23% vs 27% reference), then with the conventional dropout correction, the needed sample size per group is 150, or 300 total randomized subjects. The table below summarizes the design properties of this size study, under varying assumptions for delta, power and % missing Week 8 SIGH-D-17 assessment. The statistical testing significance level is two-sided alpha < 0.05, and the SD is assumed to be the same (7.2).

Total Sample Size	Subject SD	Delta	Power	% Missing Week 8
300	7.2	3.09	90%	23%
300	7.2	2.67	80%	23%
300	7.2	2.94	90%	15%
300	7.2	2.54	80%	15%
300	7.2	2.85	90%	10%
300	7.2	2.46	80%	10%
300	7.2	2.70	90%	0%
300	7.2	2.34	80%	0%

Detectible\* Delta for Varying Power and Missing Data Assumptions

\*Detectible delta is the smallest postulated "true" difference between means for which 80% (or 90%) of trials would be statistically significant with the given % missing Week 8 data.

All sample size calculations used Stata Version 13 software.

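### The primary model omits the number of failed adequate trials, a prognostic factor the SAP already derives at baseline; this costs a little precision but not validity

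*SAP*

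**What the plan says.** - **Prognosis.** Protocol 1.1: "Remission rates in the STAR*D trial were 36.8%, 30.6%, 13.7%, and 13.0% for each successive treatment". The last three rates correspond to patients who have already failed one, two and three treatments.
- **Who is enrolled.** Protocol 4.1 item 6 requires at least one failed adequate antidepressant trial in the current episode. Protocol 4.2 item 6 excludes patients with four or more failed pharmacologic interventions. The trial therefore spans the range of those three rates.
- **Randomization.** Protocol 5: "Randomization will be stratified by site, using a variable block size randomization to minimize bias". SAP 1.4 agrees. Treatment history is not a stratification factor.
- **Primary model.** SAP 3.4: "The model will include the fixed effect continuous factor baseline SIGH-D-17, and fixed effect categorical factors investigative site, treatment group", with visit and treatment by visit. Protocol 9.4.1 has the same model: "The model will include the fixed effect continuous factor baseline SIGH-D-17, and fixed effect categorical factors (pooled) investigative site, treatment group". The two supportive ANCOVAs adjust only for baseline SIGH-D-17 and site.
- **The factor itself.** The ATRQ is done at screening (protocol 6.4.1). SAP 3.2 tabulates by arm the "number of failed, adequate treatment regimens in the current MDD episode (1 vs > 1") and gives a dose and duration rule for it. It appears again only as a subgroup factor tested through an interaction, as 1 vs >1 in SAP 3.4 and as 1, 2, 3 in protocol 9.4.3.

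**The concern.** The plan's own background section treats treatment history as a major determinant of outcome. The variable is known before randomization and already has a programmed definition. Leaving it out of the model has two consequences.

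First, outcome differences between patients with one failure and patients with several stay in the residual variance and widen the Week 8 confidence interval. SAP 4 itself says that the planning delta of 3.1 is ambitious, that 2.5 or less is arguable, and that active comparisons can expect 1.5 or less, so precision is worth having.

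Second, if the arms differ by chance on this factor, the planned analysis has no prespecified answer to the question of whether that explains the result. An adjustment added after seeing the baseline table would carry less weight.

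**Working it through.** **1. Reproduce the plan's sample size.** SAP 4: "The sample size is calculated for the two-sided alpha=0.05, 90% power test of two independent means of improvement in SIGH-D-17", with delta 3.1, SD 7.2 and 23% dropout.
- Normal approximation: n = 2(1.960 + 1.282)² / (3.1/7.2)² = 113.4, so 114 per group. The t-test gives 114.3 to 114.6, so 115 per group, as stated.
- Dropout: 115/0.77 = 149.4, so 150 per group, as stated.
- Evaluable at Week 8: 150 × 0.77 = 115.5 per arm.
- SE of the difference: 7.2 × √(2/115.5) = 0.947. Half-width of the 95% CI: 1.96 × 0.947 = 1.86 points.

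**2. Size of the factor (assumption).** The documents give neither the variance explained nor the split between 1 and >1. As an anchor, read the remission gap as a shift on a normal scale:
- probit(0.306) − probit(0.137) = −0.507 + 1.094 = 0.587 SD, or 4.2 points at SD 7.2.
- probit(0.306) − probit(0.130) = −0.507 + 1.126 = 0.619 SD, or 4.5 points.
- probit(0.137) − probit(0.130) = 0.032 SD, or 0.2 points. Two and three failures are nearly the same, so 1 vs >1 captures almost all of it.

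With fraction f in one category and shift d, R² = f(1−f)d² / (1 + f(1−f)d²). For f from 0.3 to 0.5 this is 6.7% to 8.7%; at half the gap it is about 2%. The range 2% to 8% is used below.

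**3. Effect of adjusting.** SD_adj = 7.2 × √(1−R²), with 115.5 per arm and a two-sided 0.05 t-test.

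| R² | SD | CI half-width | Power, delta 3.1 | Power, delta 2.5 | Power, delta 1.5 |
|---|---|---|---|---|---|
| 0 | 7.20 | 1.86 | 90.3% | 74.8% | 35.1% |
| 2% | 7.13 | 1.84 | 90.8% | 75.6% | 35.7% |
| 5% | 7.02 | 1.81 | 91.7% | 76.9% | 36.6% |
| 8% | 6.91 | 1.78 | 92.5% | 78.2% | 37.6% |

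In subjects, 300/(1−R²) − 300 is about 6 at R² 2% and 26 at R² 8%.

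**4. Chance imbalance.** With 150 per arm and a 50:50 split, the SD of the between-arm difference in the share with >1 failure is √(2 × 0.25/150) = 0.058. A difference of 10 percentage points or more has probability of about 8% (about 6% at a 30:70 split). At the full gap it would shift the estimate by 0.10 × 4.2 to 4.5 = 0.42 to 0.45 points, about 14% of 3.1 and under half of the SE of 0.947.

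**5. Validity.** In 10,000 simulated trials with a 50/30/20 mix of one, two and three failures, type I error was 5.2% without the factor and 5.3% with it (simulation error about 0.2 points).

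**6. Does a main effect alone suffice?** A main effect is held equal at Weeks 2, 4, 6 and 8. If the true effect grows linearly, with b = (0.25, 0.5, 0.75, 1) of its Week 8 size, the share of the Week 8 effect removed is (1′V⁻¹b)/(1′V⁻¹1), where V is the visit covariance matrix. With equal visit SDs and a common correlation this is the mean of b, 63%. With SDs rising from 5 to 7.2 and a common correlation of 0.8 it is 9%. A factor-by-visit term is needed to obtain the gains in step 3.

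**The case against.** The strongest reply is that this is a preference for efficiency. Randomization makes the unadjusted comparison unbiased on average, and its standard error already allows for chance imbalance. The gain is at most about 0.08 points of CI half-width and could be as little as 0.02, which is unlikely to change how the trial is read. That stands, and it rules out two readings a reader might infer: that the primary test is biased or invalid, and that N=300 is too small because the factor was left out. The 7.2 used for planning is an SD of change not adjusted for this factor, and the stated sample size reproduces.

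The size is also uncertain, for reasons that mostly point downwards. The rates are remission in another study, not SIGH-D-17 change given baseline. Baseline severity and site may already absorb part of the effect. SAP 3.2 counts only adequate trials, whereas protocol 4.2 item 6 counts failed interventions, of which only one need be adequate, so a patient with three failures can be coded 1. Failure through intolerability also counts at entry. The variable is therefore not the same as the treatment step behind the cited rates.

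Protocol 1.1 may also suggest that outcome falls steeply at every step. Within the enrolled range the cited rates do not show that: the fall lies between one and two failures.

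Finally, the factor is not ignored. It is tabulated by arm, and treatment effects are shown within its levels. Neither of these supplies a prespecified overall effect adjusted for it.

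**Conclusion.** The point holds as a modest, nearly free improvement. A baseline factor that the protocol itself describes as strongly prognostic is collected and derived, but no planned analysis reports an overall treatment effect adjusted for it. At R² of 2–8%, adjustment takes the Week 8 half-width from about 1.86 to 1.78–1.84 points, power at delta 3.1 from about 90% to 91–92.5%, and power at delta 2.5 from about 75% to 76–78%. It also removes a conditional shift of about 0.4 points in the roughly 6–8% of trials where the arms differ by 10 percentage points or more, if the full remission gap carries over. That shift is a chance feature of a single trial, not a bias of the design.

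These figures rest on an assumed R², an assumed split of 1 vs >1, SD 7.2 and 23% missing at Week 8. The upper end of the R² range is more likely too high than too low.

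**What to change.** Before Main Study unblinding:
- Add failed adequate trials in the current episode (1 vs >1, as derived in SAP 3.2) and its interaction with visit to the primary MMRM and to the continuous secondary MMRMs.
- Make the change in protocol 9.4.1 and the protocol summary as well as SAP 3.4. The protocol fixes the model, so a SAP edit alone would put the two documents in conflict.
- Keep the planned subgroup interaction, and reconcile its categories (1, 2, 3 in the protocol; 1, >1 in the SAP).
- Report the currently planned model as a supportive analysis.

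Timing decides the status. Protocol 8.1 allows SAP amendments until unblinding. SAP 1.1 says version 3.0 was approved before the Main Study was unblinded and that version 4.0 leaves the Main Study analyses unchanged, but it does not show whether unblinding has since taken place. If it has, the current model stays primary and the adjusted one is supportive only.

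Extending the adjustment to the exploratory Elderly ANCOVA is optional, since simpler models were chosen there deliberately.

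The cost is four fixed-effect parameters (one main effect, three for visit), a protocol and SAP amendment, and no new data.
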